Baseline Period: During a 4-week baseline period, the participants will continue their usual activity but will wear the Garmin and ActivPAL 4 and keep a study diary. We will use this to assess their baseline PA profiles and seizure frequency and to screen for adherence with device and diary use, as participants who have <75% complete days of seizure recording or step data via the Garmin will not be randomized. A 4-week baseline period and self-report of seizures are both standard protocol in epilepsy clinical trials.[45]

Batched enrollment will be utilized to ensure large enough groups for the group coaching exercise intervention. Due to this, the time between visits may vary.

Arm 1 Exercise Intervention:

Participants in this arm will undergo a 12-week physical activity program aimed to achieve the equivalent of 8,000 steps per day (56,000 weekly steps). To ensure uptake, our intervention is rooted in social cognitive theory and led by a trained health coach, trained within the Wake Forest Behavioral Medicine Lab's Behavioral Coaching program, which follows principles of group dynamics, social cognitive theory, and self-determination theory to develop self-efficacy for behavior change, which is instrumental to building lasting behavior.

Participants will meet in small groups of 2-8 participants facilitated by a behavioral coach and, when available, a patient-stakeholder. Following randomization, the behavioral coach will contact the participants in this arm, to set up a time for each weekly video meeting. Each weekly meeting will occur within the coach's locked Webex room using a single link that will be provided to participants digitally via email. In the event of any unforeseen technical difficulties, participants can call into the Webex meeting, but this is not preferred. These sessions are developed using group dynamics principles and founded in social cognitive theory, utilizing the group structure as a tool of behavior change. Participants will act as models to one another, provide an avenue for addressing exercise barriers that arise daily, and foster a sense of accountability toward weekly activity goals.

During each weekly video meeting, the coach and participants will review the timing of the next week's meeting, modifying the timing as needed, and setting reminders if applicable.

Each group session will progress through the following tasks:

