3. Exploratory Objectives: Exploratory Effectiveness: For exploratory efficacy purposes, we will also gather pre- and post- intervention data on seizures, depression, anxiety, physical functioning, quality of life, and social cognitive mediators of behavior change via the following:

a. Exploratory Endpoints

i. Effects on seizures

1. Seizure frequency via study diary report

This has been shown to be a reliable and standard way of recording seizures in epilepsy studies. For the purposes of evaluating a change in seizure frequency, the number of seizures during the final 4 weeks of the intervention will be compared to the number of seizures during the 4-week baseline. The diaries will be returned via electronic data capture in redcap. Participants will be reminded to complete and return the diary via automated text and/or email. If diaries are not received, the participant will be called and prompted to return the study diary.

2. Seizure severity via the Liverpool seizure severity scale (LSSS)

ii. Effects on mood:

1. Depression scores

Participants will complete the Neurological Disorders Depression Inventory for Epilepsy (NDDI-E)[47]. This will be performed in-person at visits 1 and 3 only (monitoring and management of expression of suicidal ideation is outlined under Section VI below). This will be reviewed by study personnel and documented in the *Review Assurance of the NNDI-E* form

2. Anxiety scores

Participants will complete the Generalized Anxiety Disorder (GAD-7)[48, 49] in person at Visits 1 and 3 and remotely via redcap survey at Visit 4.

3. Stress scores (PSS)

Participants will complete the Perceived Stress Scale (PSS) in person at Visits 1 and 3 and remotely via redcap survey at Visit 4.

iii. Effects on quality of life

1. Quality of Life

Participants will complete the Quality of Life in Epilepsy-31 (QOLIE-31)[50]. This will be given in person as Visits 1, and 3, and remotely via emailed redcap survey link at Visit

2. Medication side effects

Participants will complete the Adverse Event Profile (AEP) at Visits 1 and 3 and remotely via emailed redcap survey link at Visit 4

iv. Effects on social cognitive theory constructs

1. To evaluate the influence of social cognitive constructs on behavior change in this population, participants will complete the Exercise Self-

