Expected Events: In this study, no serious adverse events are expected. Expected adverse events include temporary muscle soreness, temporary joint pain, and temporary increased physical fatigue when starting the exercise regimen or when increasing the exercise. Other expected events include mild discomfort from physical exertion including shortness of breath that improves when ceasing exercise and sweating. In people with asthma, an increase in the need for inhaler use is expected. In people who have a very high baseline seizure frequency, and even in those with less frequent seizures, seizures are reasonably expected to occur during exercise on occasion and certainly will occur during the course of the study. However, seizures that occur consistently with exercise in a single individual is not expected. In addition, it is not expected for participants to have a large

Protocol version:

Template updated 9.24.14

increase in seizure frequency. A small increase would be within the normal fluctuation of seizure frequency in people with epilepsy.

Specifically, the temporal relationship of seizures to exercise will be recorded in the daily study diary. Responses will be reviewed by the study team weekly. In participants who demonstrate an increase in seizure frequency from their baseline weekly frequency consistently over a 4 week period, the temporal relationship to exercise will be further investigated. In those who have increased seizure frequency AND who report a clear temporal association with exercise (seizure occurs during or immediately after exercise in 50% or more of their seizures), participation in the intervention will be halted due to concern for exercise-induced seizure activity.

All other events not listed above will be considered unexpected for the purposes of this trial. The unblinded investigator will be responsible for determining whether an AE is expected or unexpected. An AE will be considered unexpected if the nature, severity, or frequency of the event is not consistent with the risk information previously described for the study intervention.

Adverse Event Classification:

All AEs will be assessed by the study staff for severity and categorized using the criteria described below.

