Potentially Related: There is some evidence to suggest a causal relationship (e.g., the event occurred within a reasonable time after administration of the trial medication). However, other factors may have contributed to the event (e.g., the participant's clinical condition, other concomitant events). Although an AE may rate only as "possibly related" soon after discovery, it can be flagged as requiring more information and later be upgraded to "probably related" or "definitely related", as appropriate.

Unlikely to be related: A clinical event, including an abnormal laboratory test result, whose temporal relationship to study intervention administration makes a causal relationship improbable (e.g., the event did not occur within a reasonable time after administration of the study intervention) and in which other drugs or chemicals or underlying disease provides plausible explanations (e.g., the participant's clinical condition, other concomitant treatments).

Not Related: The AE is completely independent of study intervention administration, and/or evidence exists that the event is definitely related to another etiology. There must be an alternative, definitive etiology documented by the clinician.]

Adverse Event Tracking:

Adverse Events that are of special interest for this study will be actively tracked. These include worsening of seizure frequency, falls, and injuries. These will be specifically recorded by the participant in their study diary, which will be returned electronically daily.

All other adverse events will be passively collected at each study visit (visits 2-4) by asking "have you had any health problems since your last visit?"

All AEs will be captured on the appropriate case report form (CRF). Information to be collected includes event description, time of onset, clinician's assessment of severity, relationship to study intervention (assessed only by those with the training and authority to make a diagnosis), and time of resolution/stabilization of the event. All AEs occurring during the study must be documented appropriately regardless of relationship.

Any medical condition that is present at the time that the participant is screened will be considered as baseline and not reported as an AE. However, if the study participant's condition deteriorates at any time during the study, it will be recorded as an AE.

Management of Suicidal Ideation:

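### The one specified seizure-frequency comparison covers only the final 4 intervention weeks, so large early exercise-linked worsening that triggers the halt rule can be understated in it

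*Combined protocol and SAP*

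**What the plan says.** Outcome Measure(s), item 3.a.i.1, defines the seizure-frequency endpoint: "the number of seizures during the final 4 weeks of the intervention will be compared to the number of seizures during the 4-week baseline". The Analytical Plan (Aim 3) turns this into a change score and fits a linear regression with assigned arm as the effect of interest and the baseline score as covariate. The resulting effect sizes and variability are to be used in planning a larger trial.

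On timing, Arm 1 Exercise Intervention says "Participants in this arm will undergo a 12-week physical activity program", and the visit schedule places those 12 weeks at study weeks 5-16. The final 4 weeks are therefore nominal study weeks 13-16.

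The Safety and Monitoring Plan (Expected Events) contains a halt rule with two conditions, both required. The first is "an increase in seizure frequency from their baseline weekly frequency consistently over a 4 week period". The second is a clear temporal link, defined as "seizure occurs during or immediately after exercise in 50% or more of their seizures". When both hold, "participation in the intervention will be halted due to concern for exercise-induced seizure activity". The rule stops the intervention; it does not say that the participant leaves the study or stops the diary. Interventions and Interactions has all participants keep the diary for the whole study. On review of the diaries, the plan says "Responses will be reviewed by the study team weekly".

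Adverse Event Tracking lists events of special interest: "These include worsening of seizure frequency, falls, and injuries". The Analytical Plan contains no by-arm summary of these events, no count of halts, no seizure-frequency comparison for weeks 5-12, and no rule for using a halted participant's diary counts.

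**The concern.** The halt rule acts on the participants who carry the harm signal: those whose seizures rose and clustered around exercise. It can act up to 4 full weeks before the analysed window opens. For a participant halted early, weeks 13-16 are off-intervention time.

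What then enters the analysis depends on points that the plan leaves open:

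- If the diary continues and the rate falls back, the participant counts in arm 1 as little or no change.
- If the final count is missing, a complete-case regression omits the participant.

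In both cases the early worsening is understated. At stake are a planning estimate for the next trial and the completeness of the seizure-harm summary. The Background treats the idea that activity triggers seizures as disproven, so a near-zero final-window estimate could readily be taken as supporting seizure safety, with nothing in the planned analysis to show that participants had been halted.

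**Working it through.** The documents give no effect size, power or sample-size derivation for seizures, so there is no stated figure to reproduce. The check is calendar arithmetic, then a simulation that applies both halt conditions.

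**1. Calendar.** Inputs: intervention in study weeks 5-16, window in weeks 13-16, and 4 weeks of increase needed before a halt. If worsening starts in week s, the earliest halt is the end of week s + 3. The worsened on-intervention weeks inside the window number max(0, s + 3 - 12).

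| Start week s | Earliest halt (end of week) | Worsened on-intervention weeks in window |
|---|---|---|
| 5 to 9 | 8 to 12 | 0 |
| 10 | 13 | 1 |
| 11 | 14 | 2 |
| 12 | 15 | 3 |
| 13 | 16 | 4 |

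For starts in weeks 14-16 the 4 weeks cannot be completed before the programme ends, so all their on-programme worsening lies in the window. That 5 of the 12 start weeks give 0 is a statement about the calendar, not a probability.

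**2. How large an increase the rule needs.** Let b be the background rate and p the exercise-linked rate. The second condition, p / (b + p) ≥ 0.5, gives p ≥ b. With an unchanged background, the total rate must roughly double. Smaller increases meet the condition only by chance.

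**3. Simulation with both conditions applied.** Assumptions that are not in the documents:

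- Poisson weekly counts.
- A constant multiplier from week 5 until any halt, with all excess seizures exercise-linked.
- An increase is consistent if each of the 4 weeks exceeds the baseline weekly mean.
- No delay before the halt.
- After a halt, the diary continues and the rate returns to baseline.

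Baseline rates are 0.25, 1 and 2.9 per week. The last is the figure quoted under Rigor of the Prior Research for 15 women with drug-resistant epilepsy, used here only as an assumption. The columns give the mean change per 4 weeks from baseline.

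| Baseline per week | Multiplier | Halted by end of week 12 | No halt | Final window | Share kept |
|---|---|---|---|---|---|
| 2.9 | 1.5 | 8% | +5.8 | +5.2 | 90% |
| 2.9 | 2 | 63% | +11.6 | +3.5 | 30% |
| 2.9 | 3 | 99% | +23.2 | +0.1 | under 1% |
| 1 | 1.5 | 11% | +2.0 | +1.7 | 86% |
| 1 | 2 | 39% | +4.0 | +2.2 | 55% |
| 1 | 3 | 80% | +8.0 | +1.3 | 16% |
| 0.25 | 1.5 | 1% | +0.5 | +0.5 | about 100% |
| 0.25 | 2 | 5% | +1.0 | +0.9 | 94% |
| 0.25 | 3 | 20% | +2.0 | +1.5 | 76% |

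The last column is the final-window change divided by the no-halt change, taken before rounding. For example, 3.52 / 11.57 = 30%.

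With rates varying between people (gamma, shape 0.5 to 4, mean 1.5 per week), the share kept is 88-93% at 1.5 times, 31-43% at twice and about 7% at three times. The pattern is the same.

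**4. Arm level.** Up to 40 participants at 2:1 gives 40 × 2/3 ≈ 27 in arm 1. One participant whose rate doubles from 2.9 per week has 2.9 × 4 = 11.6 extra seizures per 4 weeks. If that excess is absent from the window, the arm 1 mean change loses 11.6 / 27 = 0.43 per 4 weeks.

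**5. What the whole period would show.** Using all 12 weeks, scaled to 4, the 2.9-per-week scenarios give +5.5, +7.2 and +8.3 at 1.5, 2 and 3 times, against +5.2, +3.5 and +0.1 in the final window. The 12-week figure also includes off-intervention time, but it does not lose the early weeks.

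**The case against.** The strongest reply is that this is an exploratory effectiveness endpoint, and harm has its own route. Diaries are returned daily and reviewed weekly, worsening seizures are actively tracked, adverse events are recorded with onset, severity and relatedness, and an independent committee reviews the data. Seizure severity (LSSS) has its own change score, and most outcomes are re-assessed at week 28. An end-of-period comparison by assignment that includes people who stopped is also a legitimate choice. All of this stands. A reader might infer that the plan has no other seizure analysis, or that it removes harm from the record; the documents do not support either. The gap is narrower: none of these routes gives a planned by-arm comparison of seizure frequency in weeks 5-12.

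A reader might also infer that early harm will be analysed as no change. The text does not say so. That outcome needs both halt conditions, early onset, a continuing diary and a rate that falls back. Participants with medication or device changes are to be analysed separately (Arm 2 Control section), which could apply to some who worsen.

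The timing above is the earliest possible. The plan calls for further investigation after the 4 weeks and gives no halt date, and any delay puts more worsened weeks in the window. Batched enrollment may shift the calendar. Step goals rise in increments, so the early weeks carry the lowest goals. Nothing in the documents indicates how many participants, if any, would double or triple their rate.

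**Conclusion.** The point holds in limited form. The only specified seizure-frequency comparison can miss large, exercise-linked worsening that starts in about study weeks 5-9, because the halt rule can end exposure before the window opens. At 2.9 seizures per week, the window keeps about 30% of a doubling and under 1% of a tripling. It keeps about 90% of an increase to 1.5 times, and at 0.25 per week halts by the end of week 12 occur in only 1-20% of the scenarios' participants. Smaller, later or not exercise-linked increases mostly remain counted, so a general claim of masking would be wrong.

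The sizes rest on the assumed rates, multipliers, reading of consistency, immediate halt and return to baseline. The direction rests only on the documents' windows and on exposure ending early. The result is a possibly biased planning estimate and an incomplete harm summary. The primary feasibility conclusions are unaffected, and no view is taken on the halt rule itself. This is a cheap improvement to the analysis text.

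**What to change.** Keep the final-4-week endpoint and leave the halt rule as it is. Add to the Analytical Plan, from the same daily diaries:

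- (a) The seizure rate per observed diary week over the whole 12-week intervention period, by assigned arm, in the same baseline-adjusted model, reported beside the final-4-week estimate.
- (b) By arm, the number of participants with a 4-week increase over baseline, using one stated definition applied identically to both arms.
- (c) In arm 1, the number halted under the rule and the week of each halt.

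State that halted participants' diary counts stay in the assigned-arm analysis. State also that the final-window estimate includes off-intervention time for them, and is not to be read alone as evidence of seizure safety. Items (b) and (c) are needed as well as (a), because the 12-week rate also dilutes the increase after a halt.

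A pre-halt rate in halted participants alone should not serve as an effect measure: they are selected for high counts and have no control comparator.

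The cost is a few lines of text and one more table, with no new data. The seizure result may look slightly less favourable.

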Consistent data support the use of a 7,000-8,000 step per day goal to achieve current recommendations for moderate-to-vigorous-intensity PA.[40] In numerous studies, self-selected PA intensity approximates or exceeds the minimum range recommended by the American College of Sports Medicine (ACSM).[41] In contrast, prescribed exercise intensities often result in feelings of displeasure and loss of autonomy, which interfere with the tenets of self-determination theory, thereby limiting uptake and sustainability.[42, 43] Thus, a step-goal based intervention with self-selected intensity is designed to address the unique barriers of this population, avoid undue stress (a common seizure trigger), and encourage uptake and sustainability. Our work and that of others has shown feasibility of remote interventions and wearables in PWE.[28, 44]

Objectives

Aim 1: To assess feasibility (adherence and sustainability) of a telehealth delivered, step-goal based PA intervention as measured by average daily steps achieved compared to steps assigned during the final 4 weeks of the intervention period (adherence) and the final 4 weeks of the maintenance period post-intervention (sustainability).

[figure not shown]
Aim 2: To assess the self-selected intensity distribution of activity in the intervention arm (time spent in objectively-assessed sedentary behavior, light-intensity, or moderate to vigorous intensity activity) to determine if they achieve intensities within the American Heart Association (AHA) guidelines.

Exploratory Aim 3: To explore estimates of variability of the effect size of a telehealth delivered, step-goal based PA intervention on seizures (measured by frequency and severity) and epilepsy-associated comorbidities (anxiety, depression, QOL, and measures of fitness/cardiovascular health) in the exercise group compared to the control group.

Methods and Measures

Design

A randomized, controlled trial with a two-arm, parallel group design with a wait-list education control

Protocol version:

Template updated 9.24.14

Setting

Academic medical center, Atrium Health Wake Forest Baptist

Subjects selection criteria

Adults with epilepsy will be actively recruited from the Comprehensive Adult Epilepsy Clinic at Atrium Health Wake Forest Baptist, and passively recruited from the community

Inclusion Criteria

- Age 18 or older

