1. **Introduction and ice breaker:** Participants will engage in brief tasks requiring self-disclosure as a means of opening communication for the remainder of the session.
2. **Didactic content:** Next, the coach will guide participants through weekly didactic content related to health and physical activity. These sessions are designed to reduce negative outcome expectancies related to activity (e.g., activity is unsafe, addressing how different types of movement improve health), to highlight facilitators in the environment while addressing common barriers to activity, and providing education on how activity improves health.
3. **Discussion:** Building on weekly didactic content, each session will end with a guided discussion designed to provide positive reinforcement of weekly successes, opportunities to address barriers as a group, and repertoire-development in which participants share exercise experiences they have enjoyed recently.

In addition to weekly group sessions, participants will communicate briefly one-on-one with the behavioral coach using a medium of their choosing (webex, telephone, email) to address any private concerns and to review and revise goals. Key facets of these exchanges include:

1. **Review of the previous week's goal:** The coach will review with the participant progress toward the previous week's goal. To do this, the coach will log into the Garmin Connect website using the credentials provided to the participant by the study team. The coach will emphatically congratulate goal success—thus enhancing self-efficacy through mastery experiences—and adopt a proactive tone during failures with the aim of mitigating feelings of guilt. During week 1, the conversation will instead center on understanding previous experiences with activity to guide selection of the initial goal.
2. **Selection of a new goal:** Participants will aim to progress in both intensity and duration over the course of the program. The participant and coach will select a progressive stepping goal that is challenging but attainable (increase in ~20-30% increments depending on baseline steps). They will objectively self-monitor progress toward step goals, a key self-regulatory behavior. Achievement of goals is a key *mastery experience*, the most potent input to self-efficacy, and consistently identified as the key behavioral predictor of activity behavior.[46]. Goals will be revised weekly until at least 8000

Protocol version:

Template updated 9.24.14

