Questionnaires: PSS, AEP, NDDI-E, Review Assurance of the NNDI-E, GAD-7, QOLIE-31, EXSE, EGS, MOESS, LSSS		X				X	X (with exception of NNDI-E and "Review Assurance of the NNDI-E")
HRV measurement		X	X			X	
6 minute walk test		X				X	
Exit Questions							X

*in addition to review at these visits, the study diary will also be returned daily and reviewed by weekly by a member of the study staff.

**If scheduling is a challenge, V2 can be completed over the telephone with the exercise test being conducted at the first available timepoint and prior to the intervention period

Outcome Measure(s)

1. Primary Objective: Feasibility of the intervention (Adherence and Sustainability)
 - a. Primary Endpoints
 - i. Adherence to the intervention
Adherence will be measured as the number of average daily steps achieved compared to steps assigned during the final 4 weeks of the intervention period
 - ii. Sustainability of the intervention
Sustainability will be measured as the number of average daily steps achieved compared to steps assigned during the final 4 weeks of the maintenance period
2. Secondary Objectives: To evaluate the intensity distribution in the intervention arm
 - a. Secondary Endpoints: time spend in various activity behaviors (measured by the ActivePAL4)
 - i. Time spent sedentary
 - ii. Time spent in light intensity activity
 - iii. Time spent in moderate intensity activity
 - iv. Time spent in vigorous intensity activity
 - v. Acceptability of the Intervention
Participants will answer an exit survey at Visit 4 regarding what they liked about the study and what they did not like, including reasons for missed visits or non-adherence, barriers encountered, and overall satisfaction of various aspects of the study. In addition, arm 1 will answer a questionnaire at the end of the 12 week intervention about the acceptability, tolerance and satisfaction

Protocol version:

Template updated 9.24.14

with the exercise intervention. For the main endpoint, we will use the question “How satisfied were you with the exercise intervention?” with scale of 1=VERY UNSATISFIED, 2=UNSATISFIED, 3=NEUTRAL, 4=SATISFIED, 5=VERY SATISFIED. We will calculate the proportion of subjects who answer 4 or above.

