Aim 1 To assess Feasibility, we will look at (1) adherence and (2) sustainability. Adherence, defined as the proportion of participants who achieve their assigned step goal (as measured by average daily steps via the Garmin device) over the last 4 weeks of the intervention period, will be calculated and 95% binomial confidence intervals generated. Sustainability will be calculated similarly for the final 4 weeks of the maintenance period. In each case, we will utilize a one-sided 95% confidence interval to estimate the lower bound for adherence and sustainability rates to inform future studies.

Aim 2 To assess exercise *intensity*, we will use descriptive statistics to describe the time spent in sedentary, light, and moderate to vigorous PA. We will generate confidence intervals to evaluate if the achieved intensity is within the range recommended by the AHA (150 min of moderate or 75 min of vigorous activity per week).[59] To assess acceptability, arm 1 will answer a questionnaire at the end of the 12 week intervention about the acceptability, tolerance and satisfaction with the exercise intervention. For the main endpoint, we will use the question “How satisfied were you with the exercise intervention?” with scale of 1=VERY UNSATISFIED, 2=UNSATISFIED, 3=NEUTRAL, 4=SATISFIED, 5=VERY SATISFIED. We will calculate the proportion of subjects who answer 4 or above.

To address Aim 3 (exploratory evaluation of effects epilepsy and epilepsy associated comorbidities), we will compute change scores in seizure frequency, severity (LSSS), anxiety (GAD-7), depression (NDDI-E), medication side effects (AEP), cardiorespiratory fitness (VO2 max and 6MWT), heartrate variability (HRV), sleep (total sleep time per night) and quality of life (QOLIE-31) pre- and post-intervention. We will use multivariable linear regression models modeling change score as the outcome, with intervention assignment as the main effect of interest and baseline scores as a confounding variable. We will use estimates of the effect sizes and variability for planning and power of a larger trial. For HRV parameters, we will look at high and low frequency indices, standard deviation of normal-to-normal interval (SDNN) and the root mean square of successive differences (RMSSD) indices, given their established study in PWE.[11, 12]

Similarly, we will explore for effects on social cognitive mediators of behavior change (scores on EXSE, MOEES, and EGS), following the same modeling approach.

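### Do the adherence and sustainability endpoints need a named reference step goal before they can be analysed?

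*Combined protocol and SAP*

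**What the plan says.** The Objectives state Aim 1 as "average daily steps achieved compared to steps assigned during the final 4 weeks of the intervention period (adherence") and, for the second endpoint, "the final 4 weeks of the maintenance period post-intervention (sustainability"). Outcome Measure(s) lists both as primary endpoints and describes sustainability as the "number of average daily steps achieved compared to steps assigned during the final 4 weeks of the maintenance period". The Analytical Plan turns the comparison into a yes/no score: "Adherence, defined as the proportion of participants who achieve their assigned step goal (as measured by average daily steps via the Garmin device"). It adds: "Sustainability will be calculated similarly for the final 4 weeks of the maintenance period". Each rate is reported with a "one-sided 95% confidence interval to estimate the lower bound for adherence and sustainability rates to inform future studies".

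The goals are described under Arm 1 Exercise Intervention. Coach and participant choose a "progressive stepping goal that is challenging but attainable (increase in ~20-30% increments depending on baseline steps"). "Goals will be revised weekly until at least 8000" steps/day is reached and a further rise is judged not feasible. A goal rises only after a successful week. Maintenance goals are set once 8,000 is reached and no further rise is feasible. Strategies to support adherence says that the goal is individual and made each week with the coach. The visit schedule shows coaching in weeks 5-16 only. At Visit 3, arm 1 is encouraged to keep up what it is doing, and Visit 4 is at week 28.

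**The concern.** The analysis speaks of one assigned goal, but a participant can have up to four during the adherence window. The same Garmin data could be compared with the first, the mean or the last of them, or week by week, and the yes/no result can differ.

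For sustainability the wording refers to steps assigned in a period when no coaching is shown. The only goals called maintenance goals are tied to reaching 8,000. Participants who never got there might be scored, failed or left out. In addition, an individual target can be met by someone well short of the programme's 8,000-step aim, and no rate against 8,000 is planned.

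The two rates and their lower bounds are the main product of the study and are meant to inform later trials. If different analysts could obtain different rates from the same records, a later team might misread them.

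**Working it through.** The plan gives no figure for this point to reproduce. The check is how far the readings can differ, and which of them the text supports.

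**1. Windows.** The intervention covers weeks 5-16, so its last 4 weeks are 13-16. Maintenance runs from week 17 to Visit 4 at week 28, so its last 4 weeks are 25-28. Eight weeks (17-24) lie between the two windows. These are nominal weeks; batched enrolment can shift visits.

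**2. Number of goals in the adherence window.** Weekly revision allows at most four. Because goals rise only after success, the minimum is one. Where the goal does not change in weeks 13-16, every reading gives the same answer.

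The number of successful weeks needed to reach 8,000 from baseline b, if rises of rate r compound, is ceil(ln(8000/b)/ln(1+r)):

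| Baseline steps/day | r = 20% | r = 30% |
|---|---|---|
| 5,000 | 3 | 2 |
| 3,000 | 6 | 4 |
| 2,000 | 8 | 6 |
| 1,000 | 12 | 8 |

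Participants who start low or miss weeks can still be progressing in weeks 13-16. So can those who go on rising past 8,000.

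**3. Mean goal against last goal, every goal met exactly.**
- Three compounding rises in the window, with q = 1+r: (1 + 1/q + 1/q² + 1/q³)/4 = 0.777 for 20% and 0.704 for 30%.
- One compounding rise mid-window: (2 + 2/q)/4 = 0.917 and 0.885.
- Rises as a fixed share of baseline, one in each of 12 weeks: the last four goals are 2.8, 3.0, 3.2 and 3.4 times baseline at 20%, so 3.1/3.4 = 0.91. At 30% they are 3.7, 4.0, 4.3 and 4.6, so 4.15/4.6 = 0.90.

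Compounding is an assumption. The text says the increment depends on baseline steps and does not say what the percentage is taken of.

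**4. One participant (assumed values).** Goals of 6,000, 7,200, 8,640 and 10,368, each met exactly, average 32,208/4 = 8,052. The mean goal is also 8,052, so this person is adherent on the mean-goal reading and not adherent against the last goal.

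**5. Which reading the text supports for adherence.** The Objectives and Outcome Measure(s) set an average of steps achieved against the steps assigned in the same 4 weeks. Average against average over one window is the direct reading. Using only the last goal would judge three weeks of walking against a goal not yet in force.

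**6. Which reading it supports for sustainability.** Every arm 1 participant has an individual weekly goal, whether or not 8,000 was reached, so each leaves week 16 with one. No new goal is shown after that, and the advice is to carry on as before. The last goal carried forward is then the only assigned figure available. For those who plateaued at or above 8,000 it is the maintenance goal. Because the rate is a proportion of participants, calculated as for adherence, nothing suggests dropping those without a maintenance goal.

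**7. Size.** Arm 1 is 40 × 2/3 = 26.7, about 27 at full enrolment, and 1/27 = 3.7 points. As an illustration with exact one-sided 95% bounds, 20/27 is 74.1% (lower bound 56.8%) and 19/27 is 70.4% (lower bound 52.9%). Moving one participant shifts the bound by 3.9 points, against a distance of 17.3 points between the 20/27 estimate and its bound.

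**The case for a change.** The strongest argument for a change is that these rates are the primary result and that an unwritten scoring rule can be settled after the data are seen. The principal investigator is unblinded by design. Blinded processing of the activity data helps little here, because only arm 1 has goals. The investigators may also not settle on the readings in steps 5 and 6. It is true that the text leaves the rule unwritten, and that a participant who met every weekly goal could be called non-adherent on the last-goal reading.

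A second point also stands. The two natural readings are not like for like for anyone still progressing at week 16. After three compounding rises, the last goal exceeds the window mean by a factor of 1/0.777 = 1.29 or 1/0.704 = 1.42. The participant in step 4, walking 8,052 in both windows, would be adherent and then not sustained against 10,368. If goals do not fall, the effect runs in one direction, towards a lower sustainability rate, and is confined to those still progressing.

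The rest carries less weight. That an individual goal can differ from 8,000 is inherent in the measure Aim 1 chose, and that measure is legitimate. A rate against 8,000 would be an extra summary, available from Garmin data already collected. Leaving out participants without a maintenance goal is a practice that no section suggests. The coaching manual listed in the Appendix is not among the documents and may say more about goal-setting.

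**Conclusion.** The wording gap is real, but it is missing detail and not an error. Analysts following the plan would compare the 4-week average with the mean of the goals in force, and the maintenance average with the last assigned goal, for all of arm 1. Both give sound descriptive rates.

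The readings diverge only for participants whose goal changed in weeks 13-16. For those who met rising goals exactly, the window average is 70% to 92% of the last goal under the assumptions in step 3. Each participant reclassified is worth 3.7 points at 27 in arm 1. The documents give no walking data from which to say how many would be affected, so no overall shift can be stated.

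This is a feasibility study of up to 40 people with no hypothesis test or success threshold for Aim 1, so no conclusion reverses on the choice. A report of the two rates would ordinarily say which goal was used, and the adherence and sustainability figures should be compared with the caveat above in mind. No change to the plan follows.
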